This study manipulates e-cigarette nicotine flux systematically, testing the hypothesis that abuse liability will be related directly to flux among a sample of cigarette smokers. No previous study has manipulated nicotine flux and examined within-group effects, so we could not estimate effect size. Thus, we calculated a sample size to achieve a power of >0.80 with $\alpha <0.05$ and assuming a small effect size (Cohen's $f=0.20$) and moderate repeated measures correlation ($r=0.5$) in a repeated measures ANOVA with nicotine flux as within-subjects factors (N=32; GPower). In Study 2, 40 cigarette users will attend the lab for 5 sessions - no flux, low flux, cigarette-like flux, high flux, and an own brand cigarette control (always session 5). We hypothesize that flux will be positively associated with willingness to pay/work (drug purchase task, progressive ratio task) and willingness to substitute e-cigarettes for own brand cigarettes (cross-product drug purchase task, cross-product progressive ratio task), and inversely to price sensitivity (drug purchase task) for all smokers.

It is possible that we would consent up to 100 participants in order to obtain 40 participants who complete the entire study.

4. * List the study inclusion criteria:

All participants must be healthy (determined by self-report), between the ages of 18-55 (verified by photo ID), willing to provide informed consent, and attend the lab and abstain from tobacco/nicotine as required. Participants must agree to use designated products according to the study protocol.

Participants must use at least 5 cigarettes per day if they are not classified as dual users of inhaled tobacco products.

Participants classified as dual users of inhaled tobacco products must meet at least of two definitions described below:

- at least some day use of cigarettes (≥ 3 days per week at any cigarettes per day frequency) AND
- daily use of another inhaled tobacco product (e.g., e-cigarettes, cigars, pipe)

OR

- daily use of cigarettes (at any cigarettes per day frequency) AND
- at least some day use of another inhaled tobacco product (e.g., e-cigarettes, cigars, pipe; ≥ 3 days per week at any frequency).

Participants must have a 'positive' cotinine cassette result to verify nicotine use.

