1. * Describe the study hypothesis and/or research questions. Use lay language whenever possible.

The purpose of this study is to determine if abuse liability indices will be impacted by differences in electronic cigarette (ECIG) nicotine flux among current combustible cigarette users. Nicotine flux will be controlled by using an electronic cigarette with constant device settings (30 Watts; 2 second puff duration) and different e-liquid concentrations (0 mg/ml, 6 mg/ml, 15 mg/ml, and 30 mg/ml). We will compare abuse liability indices between ECIG conditions as well as for own brand cigarette smoking.

We hypothesize that as nicotine flux is lowered, abuse liability indices will be lowered, as assessed by less willingness to pay/work for ECIG puffs and more price sensitivity.

We also hypothesize smokers will substitute from own brand cigarettes to ECIGs more quickly for ECIGs with nicotine flux conditions that most closely approximate the flux produced by cigarette smoking.

2. * Describe the study's specific aims or goals. Use lay language whenever possible.

The aim of this study is to better understand how ECIG nicotine flux impacts several behavioral economic measures of abuse liability.

Results will be used to inform future tobacco product regulations of these ECIG liquid and device features/characteristics.

3. * Choose all types of recruitment materials that may be used and upload them below:

- E-mail invitations**
- Phone Solicitation scripts (i.e. cold calls or random-digit-dialing)
- Fliers, Mailed Letters or Newspaper/TV/Radio Ads**
- TelegRAM announcements**
- Website text**
- Study-specific web sites (provide the design and text)
- Social Media**
- EPIC MyChart Patient Portal research study descriptions
- Psychology Research Participant Pool (SONA) study descriptions
- Scripts for announcements made to groups
- Other recruitment document
- No recruitment materials

4. * Describe the study procedures/methods for identifying and recruiting participants. Address all of the following three aspects of recruitment in your response.

1. Identification of potentially eligible participants or secondary data/specimens of interest.

- What database(s) will be queried to identify secondary data/specimens
- How VCU Informatics or VCU IRDS will be used for cohort identification (when applicable, see help text)
- How potential participants' contact information will be obtained

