6. * Since a separate protocol document is not uploaded, describe the proposed research using language understandable to those IRB committee members whose expertise is not scientific. The description must include:

- 1. A statement explaining the study design**
- 2. A detailed description of all the procedures that will be followed to carry out the study, preferably in sequential order, and in sufficient detail that the study's methods could be replicated**
- 3. The schedule and frequency of when and how procedures will be conducted (e.g. in person, online, phone, paper, etc.)**
- 4. A description of all research measures/tests/interventions that will be used, including analyses/tests conducted on specimens/biological samples (if applicable)**

See the help text for additional guidance

Overview. This study involves 40 CIG users who will complete 5, within-subject, laboratory conditions that differ by the product used: 1) 30 W; 0 mg/ml; 2 sec puff, 2) 30 W; 6 mg/ml; 2 sec puff, 3) 30 W; 15 mg/ml; 2 sec puff, 4) 30 W; 30 mg/ml; 2 sec puff, and 5) own brand (tobacco cigarette). The first 4 ECIG conditions will be Latin-square ordered and single blinded such that the participants will not know which condition is administered in each ECIG session. The last condition for all subjects will be their own brand CIG.

Participants. A total of 40 adults (ages 18-55) who currently use CIGs will be enrolled. We will attempt to recruit an equal number of men and women of diverse racial/ethnic backgrounds, although this study is not intended to address gender or race/ethnic differences.

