Recruitment and Enrollment. Potential participants will be recruited by IRB-approved advertisements, as well as referral from current participants. Once initial screening is completed (either over the phone or via the internet), potentially eligible participants will be invited to the lab to complete in-person informed consent, additional screening, and familiarization with study procedures (approximately 2 hrs, \$15 compensation). Once participants have been seated in a private study room, research staff will communicate with the participants primarily using Zoom as an intercom, to speak/interact with participants. Prior to in-person data collection, staff will review the informed consent in person and/or using a Powerpoint/video tool to ensure they understand the study, its risks and benefits, and their rights as research participants. Participants will have the opportunity to ask questions to the research staff, prior to signing the consent document. Following documentation of informed consent, participants will complete baseline measures to confirm eligibility, have their blood pressure and heart rate checked, provide a urine sample that will be tested for cotinine level (to confirm current smoking status) and pregnancy (women only), and provide a exhaled breath carbon monoxide (eCO) sample. Age will be verified by asking participants to provide some form of identification that includes a date of birth. Photos of participant cigarette packs will be taken. All study procedures will be reviewed/practiced using approved measures and/or Powerpoint/video-based tools. Participants will complete the Minute Discounting Task and finally the Balloon Analogue Risk Task (BART). Depending upon task performance, participants will receive up to \$40 in compensation for the actual amount earned at the end of the BART task.

New recruits will replace participants who do not complete the study. Accrual ends when the required number of completers (N=40) is reached.

Individuals whose blood pressure levels are elevated (>=140 mmHg systolic or >=90 mmHg diastolic) during screening or at a session will be provided with a blood pressure information sheet by the research staff (see study document). This sheet will be provided at the first instance of elevated blood pressure observed during the study.

Products. Own brand tobacco cigarettes will be purchased locally following enrollment by VCU approved staff. For all

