Data analysis. Subjective, physiological, DPT, CP-DPT, PRT, and CP-PRT data will be prepared as reported elsewhere ([name] et al., 2017; Rusted et al., 1998; [name] et al., 2010). Elasticity is estimated using an exponential demand function with nonsystematic DTP data excluded based on two criteria: trend, or whether the participant had a general decrease in consumption from the lowest to highest price; and bounce, or whether a participant reported higher consumption at sequential higher prices (Stein et al., 2015). In general, analysis will involve a mixed (between- and within-subject) ANOVA. Demographic data will be examined to determine if there are significant between-group differences on measures that may be related to study outcomes. Unexpected between group differences will be considered as potential covariates in the primary analysis (see Evans et al., 2006). Statistical analyses may utilize regression, ANOVA, or mixed linear models. Adjustments for sphericity violations and post-hoc testing using Tukey's HSD or planned contrasts with Bonferroni corrections will be used (Keppel, 1991). Based upon the type and amount of missing data, we may use accepted techniques such as multiple imputation (Allison, 2001).

7. * The IRB only reviews research activities, so indicate for each of the study activities described in the question above or in the protocol which activities are:

- Being performed exclusively for research purposes (i.e. they would not otherwise be done apart from this study) **VERSUS.**
- Alterations of routine activities/procedures (e.g. the study is altering the timing, frequency, method, location, amount, etc.) **VERSUS.**
- Being done for other purposes and whose data/results will be used secondarily in the study (e.g. standard medical or psychological tests, routine education practices, quality improvement initiatives, etc.).

See the help text for additional guidance

All of the procedures described above are performed exclusively for research purposes. There are no alterations of routine procedure and no procedures would be performed if these individuals were not taking part in this research study.

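### On the planned-contrast route, Holm's step-down adjustment would give the same familywise error control as Bonferroni and never less power: a cheap improvement, not a correction of an error

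*Combined protocol and SAP*

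**What the plan says.** The protocol's data analysis paragraph (Study Procedures, item 6) gives two routes after the main model: post-hoc testing by Tukey's HSD, or "planned contrasts with Bonferroni corrections will be used". No step-down variant is mentioned. The contrasts are not listed, and the paragraph does not say whether a family is formed per outcome or across outcomes.

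The hypotheses (Study Procedures, item 1) give only the general intention: "We will compare abuse liability indices between ECIG conditions as well as for own brand cigarette smoking". Participants "complete 5, within-subject, laboratory conditions that differ by the product used": four ECIG liquids (0, 6, 15 and 30 mg/ml) and own brand cigarettes in session 5. The cross-product tasks (CP-DPT and CP-PRT) are omitted from session 5, so among the behavioral tasks an own-brand contrast exists only for the DPT and the PRT.

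The sample size justification (Study Population, item 3) rests on an omnibus repeated-measures ANOVA "with nicotine flux as within-subjects factors (N=32; GPower"), with f = 0.20 and r = 0.5. "Accrual ends when the required number of completers (N=40) is reached". No power is stated for any corrected contrast.

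**The concern.** Unqualified, a Bonferroni correction ordinarily means the single-step form: each of m contrasts is tested at 0.05/m. Holm's procedure starts at the same threshold for the smallest p-value and relaxes to 0.05/(m-1), 0.05/(m-2) and so on for as long as each test rejects. It needs no assumption of independence or sphericity. As a set of tests it therefore dominates single-step Bonferroni.

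This matters somewhat here because the questions a regulator would ask (which flux levels differ from none, and which ECIGs fall short of the participant's own cigarette) are answered by contrasts and not by the omnibus test. The advantage of a step-down procedure grows when several effects are real, which is what a graded flux hypothesis predicts.

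**Working it through.** **1. Reproduce the plan's figure.** For a one-group within-subjects ANOVA with m conditions, λ = f²·n·m/(1−r), df1 = m−1 and df2 = (n−1)(m−1), with sphericity.

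- n = 32, m = 5: λ = 0.04 × 32 × 5 / 0.5 = 12.8, df 4 and 124, power 0.814. At n = 31 the power is 0.799, so 32 is the minimum and the stated N reproduces with five conditions.
- n = 40, m = 5: λ = 16, power 0.902.

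These are omnibus powers and say nothing about individual contrasts.

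**2. Inputs for the contrasts.** From the plan: 40 completers, r = 0.5, f = 0.20, alpha 0.05. Assumed: two-sided tests, unit SD, f = 0.20 applied to the four ECIG means, the contrast families, and the own-brand difference (the documents give none). The SD of a paired difference is √(2(1−0.5)) = 1, so each contrast is in SD units.

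- Equally spaced means: spacing d satisfies 1.25·d² = 0.04, so d = 0.179. The contrasts against 0 mg/ml are 0.179, 0.358 and 0.537.
- Means proportional to concentration: deviations from 12.75 are −12.75, −6.75, 2.25 and 17.25, with root mean square 11.30 and scale 0.20/11.30 = 0.0177. The contrasts against 0 mg/ml are 0.106, 0.265 and 0.531.

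**3. Thresholds.** Bonferroni tests at 0.05/3 = 0.0167 for three contrasts and 0.05/7 = 0.0071 for seven. Holm begins there and relaxes towards 0.05.

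**4. Simulation.** Multivariate normal outcomes, paired t-tests, 100,000 trials per row. Mean power is over the truly non-zero contrasts.

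| Assumed family and means | Bonferroni | Holm | At least one rejection (both methods) |
|---|---|---|---|
| 3 contrasts vs 0 mg/ml, equal spacing | 0.44 | 0.49 | 0.84 |
| 3 contrasts vs 0 mg/ml, spaced by concentration | 0.35 | 0.38 | 0.81 |
| 7 contrasts, equal spacing, own brand 0.5 SD above best ECIG | 0.657 | 0.736 | about 1.00 |
| 7 contrasts, spaced by concentration, own brand 0.5 SD above best ECIG | 0.636 | 0.694 | about 1.00 |
| 7 contrasts, four ECIGs equal, own brand 0.5 SD higher | 0.63 | 0.67 | 0.90 |

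The family of seven is the three contrasts against 0 mg/ml plus own brand against each of the four ECIGs. With equal spacing in that family, 15 versus 0 rises from 0.30 to 0.46, and own brand versus 30 mg/ml from 0.63 to 0.76.

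**5. Other families** (equal spacing, f = 0.20, 40,000 trials each). All six ECIG pairs: 0.256 to 0.280. Three adjacent ECIG pairs: 0.096 to 0.098. All ten pairs with own brand 0.5 SD above the best ECIG: 0.476 to 0.522.

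**6. Error control.** With six ECIG contrasts, familywise error is 0.042 for both methods when all means are equal. With only one ECIG mean shifted it is 0.023 for Bonferroni and 0.034 for Holm. Holm rejected every contrast that Bonferroni rejected in every simulated trial.

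**The case against.** Four points on the other side stand.

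- Bonferroni is only one of two listed routes. If Tukey's HSD is used, this point does not arise.
- The contrasts are not in the plan. The main hypothesis is directional, and a single linear trend contrast could test it. With equal spacing its noncentrality is 0.894/√2.5 × √40 = 3.58 on 39 df, giving power 0.94. With one contrast the two corrections are identical.
- The gain on ECIG contrasts is modest at the planned effect size, and for adjacent pairs it is negligible.
- Single-step Bonferroni gives simple simultaneous confidence intervals that match its tests. Holm does not.

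A reader might infer something stronger: that the plan contains an error, or that real differences are being lost for nothing. The documents support neither. Error control is sound, no stated figure depends on the correction, power is claimed only for the omnibus test, and Holm changes nothing until one contrast has already passed the Bonferroni threshold. The matching intervals are also a real benefit.

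A reader might also quote a gain of about 10 points for own brand (0.70 to 0.80). That figure needs own brand against four equal ECIGs to be a separate family of four. The plan defines no such family, and equal ECIGs would mean that flux has no effect. In one family of seven the same effects give about 4 points.

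What the objection does not remove is the dominance result itself, which is a theorem and holds for any family of two or more contrasts.

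**Conclusion.** The point holds as an optional improvement to the planned-contrast route. Holm offers the same strong familywise control and never less power. Under the assumptions in the table, the gain in mean power is about 3 to 5 points for the three contrasts against 0 mg/ml, 6 to 8 points for a family of seven with graded ECIG means, and about 4 points for own-brand contrasts if the ECIGs do not differ. It is smaller for some other families and zero for a single contrast. The chance of finding at least one difference is unchanged. Gains on own-brand contrasts concern only outcomes measured in session 5, so not the CP-DPT or CP-PRT. The families and the own-brand effect are assumptions, so these figures show the order of magnitude and are not predictions.

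**What to change.** In the data analysis paragraph, replace the Bonferroni phrase with: *planned contrasts with Holm step-down adjusted p-values within each outcome's contrast family*. In the same edit, list the contrasts for each outcome and show that own-brand contrasts are not defined for the CP-DPT and CP-PRT. The list is needed in any case, because neither correction can be applied until the family is fixed. If analysis has already begun, label the change as post hoc.

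The cost is one phrase and a short list, and Holm adjustment is a standard software option. The downside is that Holm has no equally simple matching simultaneous intervals. Where such intervals are wanted, report them at Bonferroni width and note that an interval may include zero for a contrast that Holm rejects.

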- Drug(s) / Biologics / Supplement(s) / Other Compounds (investigational products or products whose administration is dictated by the study protocol and not per the physician's clinical judgment)
- IV contrast administration for research-related imaging (will branch to the Drugs page)
- Placebos
- Safety and/or effectiveness evaluation of Bio-Medical Device(s), including in-vitro diagnostic devices/assays, mobile medical apps, software functions, and HUDs used in clinical investigations
- Washout Periods
- Expanded Access – Treatment Use of an Investigational Product
- Medical or Surgical Procedures (eg: physical exam, clinical procedures, scans, etc)**
- Specimen/biological sample collection**
- None of the Above

2. * Select all of the following types of interactions and methods of data collection that apply to this study (selections will branch):

- Surveys / Questionnaires /Written responses to questions (including data entry)**
- Active Internet data collection (i.e. using the internet to collect data, including online surveys, data collection via Zoom, apps, etc.)**
- Passive Internet data collection (i.e. passively observing online behavior, bots)
- Interviews / Focus Groups / Verbal responses to questions
- Audio / Video recording or photographing participants**
- Observations**
- Educational Settings/Assessments/Procedures
- None of the Above

3. * Select all types of recordings that will be made:

- Audio**
- Video**
- Photographs

4. * Describe the purpose of the recordings, who will be recorded and when such recordings will occur:

We will be using Zoom as an intercom for communications with participants during in-person screening and study sessions. Sometimes, such as when explaining procedures or answering questions, research staff may notify participants and then switch the camera on the participant computer 'on' so that we can facilitate a face to face conversation. Other times, all cameras may be off and/or research staff may have only their computer camera 'on' so that participants can see the researcher.

Zoom will not be recorded or stored or linked to participant IDs or used for any analysis purpose other than facilitating face to face communications in combination with social distancing.

5. * Select all types of secondary information and/or specimens that apply to this study (selections will branch):
See the help text for definitions.

- Individually Identifiable Health Information (PHI)
- Secondary data/specimens NOT from a research registry or repository
- Information/specimens from a research registry or repository (Usage Protocol)**
- Information/specimens originally collected for a previous research study
- Publicly available information/specimens
- Government-generated or collected information that was or will be obtained for nonresearch activities [only applicable to research conducted by or on behalf of a Federal department or agency]
- No secondary data/specimens will be used

Behavioral Intervention/Task Details

This page asks for details about the social/behavioral intervention, task, or environmental manipulation in the research.

Interventions include both physical procedures by which information is gathered and manipulations of the subject or the subject's environment that are performed for research purposes. This might include activities such as playing computer games, performing a task, thought/cognition activities, environmental manipulations, and educational activities.

If the study only involves surveys, interviews, or secondary data collection, go back to the Project Details page and uncheck "Social/Behavioral interventions or experimentation / Tasks / Environmental manipulations" in Question 1.

1. * Describe the duration of the social/behavioral intervention, task, or environmental manipulation:

This study has a total of five sessions. The first four sessions are about 3 hours and 40 minutes. The final session is slightly shorter, lasting about 3 hours.

2. * Describe any potential harms or discomforts that participants could experience during the intervention activity:

Physical Risks:

1. You may experience some mild discomfort during the 12-hour tobacco/nicotine abstinence period before each session. Side effects from tobacco/nicotine abstinence can include irritability, anxiety, restlessness, excessive hunger, difficulty concentrating, and sleep disturbance. Though uncomfortable, these feelings are not medically dangerous.
2. You may experience mild frustration while completing some of the study-related tasks.
3. On very rare occasions, you may experience small droplets of liquid during inhalation of the e-cigarette we provide. You may find these droplets to be unexpected and/or unpleasant. This experience has been reported by e-cigarette users, and they report that it is an annoyance that does not appear to present any known medical danger. If this occurs, we will immediately replace the e-cigarette device you are using.
4. The e-cigarette liquid that we give you may contain more nicotine than you are used to, although some e-cigarette users report using these liquids. Inform the study staff immediately if you experience any discomfort
5. You may also experience side effects from products that contain nicotine such as acute increases in heart rate and blood pressure, sweating, lightheadedness, dizziness, nausea, and nervousness. These side effects are unlikely in individuals who use cigarettes regularly.
6. The Centers for Disease Control and Prevention advises that e-cigarette, or vaping products are unsafe for youths, young adults, or women who are pregnant. Adults who do not currently use tobacco products should not start using e-cigarette, or vaping, products. If you use e-cigarette products, monitor yourself for the below symptoms and promptly seek medical attention if you have concerns about your health.
 - a. Some people who use e-cigarettes have reported experiencing seizures. Some of these individuals reported a prior history of seizures or using other substances at the same time as their e-cigarette.
 - b. In some cases, e-cigarette use has led to respiratory illnesses such as difficulties breathing, shortness of breath, cough, and/or chest pain before hospitalization. In some cases, e-cigarette use has led to death, although most of these cases have been related to vaping THC.
 - c. In some cases, e-cigarette use has been associated with symptoms of mild to moderate gastrointestinal illness such as nausea, abdominal pain, vomiting, diarrhea, fevers or fatigue.
7. The use of e-cigarettes may include other side effects/risks such as a sore or scratchy throat and headache.
8. E-cigarette devices will be reused for participants. New disposable mouthpieces will be provided to each participant. There is some risk of contamination or illness, which is minimized by sanitizing the e-cigarette devices in addition to the use of these mouthpieces.
9. The researchers will let you know about any significant new findings (such as additional risks or discomforts) that may make you change your mind about participating in the study.

Non-physical Risks

1. Participation in research might involve some loss of privacy. There is a small risk that someone outside the study could see and misuse information about you.
2. The study questionnaires ask personal questions that are sensitive in nature. You may refuse to answer any question that makes you feel uncomfortable.

3. * Will the intervention activity be physically invasive or painful?

Yes
 No

4. * Describe the impact the intervention activity will have on participants, including the nature and duration of any impact(s):

Participants will be using an ECIG/cigarette that contains nicotine. They may experience the effects of nicotine use which could include acute increases in heart rate and blood pressure, sweating, lightheadedness, dizziness, nausea, and nervousness, although these are less likely in individuals who use nicotine-containing products regularly. All of the participants are experienced, cigarette smokers. The duration of these impacts is expected to be no longer than the length of the session.

5. * In the investigator's opinion, is there any reason to think that the participants will find the intervention activity offensive or embarrassing? Explain why or why not.

No.

Sample Collection Details

1. * Select all of the types of samples that will be collected as part of this study.

- Amniotic Fluid
- Blood
- Buccal Smears
- Saliva
- Tissue
- Urine
- Stool
- Other

2. * If Other, please describe the type of sample being collected:

Upon arrival at the laboratory for the research session, participants' eCO will be measured to ensure compliance with the overnight abstinence criteria. Samples will not be stored.

3. * In order to collect urine, will an indwelling catheter be placed solely for the research study:

- Yes
- No

4. * Describe how the sample will be collected and the collection schedule. For each type of sample, include information about

- The procedures that will be followed to collect the sample
- The role(s) of the individuals who will collect the sample
- The volume/size range of the sample
- The timing and frequency of sample collection

Urine will be collected during the baseline screening to test for recent nicotine exposure and for current pregnancy for women. About 30 mL is required for testing purposes, participants may provide more but it is not required. No urine is saved. Participants will be given a urine collection cup to collect their own urine in a nearby bathroom and return to the laboratory space (<20 ft away) where the specimen will be processed. After screening tests have been completed the urine sample is disposed of via toilet and the urine collection cup is disposed of in the garbage.

5. * Will genetic testing or genetic analyses be conducted on any of the samples:

- Yes
- No

Active Internet Data Collection

1. * Describe the platform/technology chosen for collecting the data and transmitting data securely over the internet. If proposing a non-VCU approved platform, give the rationale for selecting the technology instead of a VCU-approved platform.

Screening (baseline), session, and follow-up data will be collected and stored using the REDCap database which is located on a category one secured database at VCU. Viewing of the REDCap project will be restricted to personnel associated with this protocol.

2. * Describe how data will be linked or unlinked to identifiers including email addresses, names, and/or IP address.

If a participant enrolls in this study, they are given a numeric code (the study ID) that is connected 1) to their consent (i.e., name) via a paper key, 2) added to their registry information (the registry ID), via a separate variable in our administrative forms connected to each registry via an electronic key, and 3) their contact information which use to send the follow-up survey.

The study ID appears on all subsequent documents/data forms.

The paper key is maintained in the study binder so that we can demonstrate that a particular data set is associated with a particular consent document. This paper key and consent documents are stored separately from each other and separately from all data (under double lock).

The electronic key is maintained in the registry project and the study project where participant contact information is stored. This key will be deleted when data collection for the study has been completed.

3. * How will you protect your data collection from fraudulent responses:

The majority of measures/sessions are completed in the laboratory. Thus, we are able to monitor how participants are answering questions and ask for clarification if an answer conflicts with another answer for example. Only the follow-up survey (which has a participant unique link) is administered outside of the laboratory.

4. * Is there an alternative method for completion of the data collection other than the internet?

Yes
 No

5. * If yes, describe the alternative(s).

Study forms/measures can be completed on paper if necessary during in-person assessments.

For the follow-up forms, the alternative is to complete these forms verbally over the phone.

6. * Describe how individuals will be able to skip or not answer particular questions. If any questions are mandatory, provide justification.

Participants can skip other questions administered during the baseline session except for those required for eligibility purposes.

During study sessions, we will require responses to the symptoms experienced since last study visit questions. This allows study staff can assess a participant's recent symptoms to continue with the scheduled sessions. If a participant does not want to answer a question, they can inform study staff who can note this and remove answers (we require responses in subjective questionnaires as we find if we do not this leads to missing questions by mistake).

7. If not including children, describe any procedures used to verify that research participants are adults.

We ask participants for their age and date of birth several times (telephone or online screening, in-person screening) and verify that the answers are the same. We will also check ID during the in-person screening to verify that the participant is eligible.

Secondary Data/Specimen Details

1. * Describe the source(s) and nature of the information/specimens being obtained. This response should:

- a. Identify where the data/specimens will come from (e.g., another researcher's registry, pathology lab, commercial source, medical records, etc.); and
- b. List what types of specimens will be obtained (when applicable); and/or
- c. List all data elements that will be obtained (when applicable). A data collection form or other documentation may be uploaded and referenced here.

1. CSTP Overall Screening and Registry and the Behavioral Health Research Laboratory Screening and Registry will be used to pre-screen/determine initial eligibility for participants.

2. No data will be obtained from these protocols or transferred to the current protocol. Staff from the two registry projects will review participant responses and document on an administrative form whether they meet eligibility requirements for the current protocol.

3. No data will be obtained but current staff on this protocol will access the administrative form of either registry and use this information to contact potentially eligible participants. This includes accessing contact information (name, phone, email address), provided by participants within each respective registry survey/REDCap Project. Eligibility information and contact information will not need to be transferred or exported from either project.

The staff of HM20018290 who contact participants will also be staff on HM20002567/HM20007677. Please note, we are filling out the eligibility admin form as registry staff (not staff on this study). Participants who join the registry and complete the screening survey are evaluated for potential eligibility across all currently approved projects by approved registry staff. Registry staff responses regarding their eligibility for the present study are used to determine whether individuals are contacted for an in-person screening appointment where all eligibility criteria are evaluated again

2. * Describe whether any agreement exists between you and data/specimen provider that states you will never have access to the ability to identify the participants (i.e. access to identifiers or the code key) and that you will not attempt to re-identify individuals.

Each registry contains identifying information such as names/phone numbers/email addresses.

If a participant enrolls in this study, they are given a numeric code (the study ID) that is connected to their registry information (the registry ID), via a separate variable in our administrative forms connected to each registry. Thus each participant will have a registry ID as well as a study ID (specific to this protocol). Adding the study ID from this usage protocol to a registry is a form of an electronic key, and as it will be a separate variable in an administrative form, it can be deleted once the usage protocol is complete. The purpose of this link between the registry and this usage protocol is to help us keep track of which participants are participating in which usage protocol. No data from this usage protocol will be transferred to the registry (other than the study ID).

3. * When the information/specimens were originally collected, did individuals provide consent for secondary research use of their data/specimens (i.e. consent to another research study or to a research registry)?

Yes
 No

4. * Provide name(s) of the registry/repository being accessed.

CSTP Overall Screening and Registry
Behavioral Health Research Laboratory Screening and Registry

5. * Site having responsibility for the management of this registry/repository:

VCU
 Non-VCU

6. If the registry / repository is located at VCU, provide the IRB number for the registry / repository.

HM20002567; HM20007677

7. * Is the original consent form that participants signed upon entry into the registry /repository available?

Yes
 No

8. If YES, the original consent is available, upload it for the IRB to reference

Document Name	Document	Version	Date Modified By	Uploaded Type	Approved
View Informed Consent	P3 FLUX_Informed Consent_12.07.2022_CLEAN.pdf	0.29	2/27/2023 12:23 AM	[name] Consent/Assent/Information Sheet	Yes

Document Name	Document	Version	Date Modified	Uploaded By	Type	Approved
View Consent - Tool	P3FLUX_Consent_Presentation_12.07.2022_CLEAN.pptx	0.13	12/7/2022 2:37 PM	[name]	Other	Yes
View Text, Email, Call Scripts	Phone_e-mail_text scripts_CLEAN_12.07.2022.docx	0.19	12/7/2022 2:35 PM	[name]	Other	Yes
View COVID-19 Questions	NO LONGER USING_COVID_Questions_P3_12.07.2022.docx	0.06	12/7/2022 2:33 PM	[name]	Other	No
View Information about Blood Pressure	BP results P3 flux 8.22.2022.docx	0.01	8/22/2022 11:43 AM	[name]	Other	Yes
View P3 Flux Advertisement for CSTP Website	P3 FLUX Description for CSTP Website_CLEAN_03.30.2022.docx	0.05	4/13/2022 10:36 AM	[name]	Recruitment/Advertising	Yes
View Referral Program Card Template	P3_Referral program card_1.13.2022.docx	0.01	1/14/2022 11:49 AM	[name]	Recruitment/Advertising	Yes
View Baseline Self Report Physio Measures	P3- FLUX_Baseline forms All_5.21.2021_CLEAN.docx	0.14	5/24/2021 2:01 PM	[name]	Research Measure	Yes
View Follow-up Survey	P3-FLUX-Follow-up_05.21.2021_CLEAN.docx	0.11	5/24/2021 1:59 PM	[name]	Research Measure	Yes
View CP-DPT & DPT - Tool	DPT_CDPT presentation_04.26.2021_CC.pptx	0.03	4/26/2021 4:36 PM	[name]	Other	Yes
View DPT/CP-DPT - DPT_CDPT presentation_04.26.2021_CC.mp4 Tool VIDEO	DPT_CDPT presentation_04.26.2021_CC.mp4	0.02	4/26/2021 4:35 PM	[name]	Other	Yes
